
1.4 How will the results of this trial be used?

If the phase III trial is positive, we need to ensure that all thermally injured patients receive intravenous vitamin C. If negative or no effect, we need to ensure that patients no longer receive such therapy, even if it works in other diseases such as sepsis. As it relates to critical care

nutrition practice in general, we have a long history of practice-changing initiatives that can be tailored or adapted for use in local burn centers. We have a process of synthesizing (in the form of evidence-based clinical practice guidelines) and disseminating best practice ideas (in the form of web-based repository of tools and information [see www.criticalcarenutrition.com]). In addition, we have conducted several large cluster RCTs⁶²⁻⁶⁴ to introduce system-changing practices in ICUs in North America and several large-scale quality improvement audits of practice to define and improve current practice.^{65,66}

Over the past several years, we have discussed this program of research and this specific protocol at the annual American Burn Association (ABA) meeting with society leaders, researchers, and the burn community at large. We have leveraged our relationships with the ABA to further facilitate our knowledge translation initiatives and increase the likelihood of the uptake of research results across the world. In the fall of 2014, we conducted our latest international nutrition audit and over 200 ICUs and more than 30 burn units worldwide participated in this quality improvement activity. This activity will both strengthen our clinical trials network and enhance our ability to translate findings to other centers worldwide at the completion of this study.

1.5 Describe any risks to the safety of the participants involved in the trial.

The safety profile for vitamin C in ICU patients is remarkably favourable.⁶⁷ Real-time in the field monitoring of safety events has not revealed any safety issues (personal communication, McGuff Pharmaceuticals, Inc., Department of Regulatory Affairs, Ascor® (Ascorbic Acid Injection, USP) PADER Synopsis, Year 5, NDA 209112). However, there are several complications that may develop which will be closely monitored as ‘Events of Interest’ or outcomes in this trial. One of the potential risks is the formation of calcium oxalate crystals in renal tubule. However, this occurs at much higher doses than those being tested in the VICToRY Trial. Cancer patients, for example, sometimes receive vitamin C doses approximately 40-50 times greater than the dose we are planning to administer albeit over a longer period of time.^{68,69} We will nonetheless monitor acute kidney injury (as an outcome in this trial).

Another potential risk, albeit rare, is factitious hyperglycemia as recorded by capillary blood sugar point-of-care devices as the molecular structure of vitamin C and glucose are similar. This phenomenon does not occur with core lab assays and some point-of-care devices.^{70,71} Accordingly, we are going to mandate that glucose can only be measured with one of the 3 following systems up to 7 days after the last dose of the investigational product (even if patient is transferred on ward) : 1) core lab, 2) point-of-care arterial blood gas machine that has been validated in the setting of high plasma concentrations of vitamin C, 3) Nova Biomedical StatStrip glucometer that has been validated to be accurate in the presence of high concentrations of ascorbic acid. Episodes of true hypoglycemia (<3.8 mmol/L) will be captured in the case report form.

Since the solution containing vitamin C is acidic and contains sodium, acid-base and electrolyte imbalances are theoretically possible,⁷² but its effect on blood pH has been called “negligible” in patients receiving up to 8 g/m².⁷³ and metabolic acidosis has been reported in single-cases when multiple factors such as exsiccosis, acute kidney injury and other metabolic derangements occur simultaneously.^{74,75} Lastly, vitamin C may be associated with hemolysis in patients with glucose-6-phosphate dehydrogenase (G6PD) deficiency, who will therefore be excluded from participating in the trial. However, since the prevalence of G6PD deficiency is low in most if not all participating centers and since the trial is designed to facilitate early

administration to maximize benefit, we will not screen eligible patients for G6PD deficiency. Of note, most existing trials of intravenous vitamin C for sepsis have not screened for G6PD deficiency; no related adverse event has been reported thus far.⁴⁹ Hemolysis will be monitored and recorded in the case report form. If hemolysis happens during the intervention period, we will stop the study drug and provide standard supportive care (e.g. monitoring of hemoglobin, red blood cell transfusion as needed). Drug-induced hemolysis resolved when the causative drug is stopped.

Since no drug interactions have been reported in the previous studies on vitamin C used for the treatment of septic patients, we do not anticipate any drug interactions.

How will safety concerns be handled?

- 1) We will exclude patients with known G6PD deficiency.
- 2) For individual subjects, the treating physician will have the right to discontinue study product if the enrolled patient develops a new diagnosis of oxalate kidney stones, severe hemolysis, severe acid-base/ electrolyte imbalances or refractory hypoglycemia or any other medical complication such as an SAE that, in the opinion of the treating physician, ongoing use of study product would compromise patient safety.
- 3) We have a Data Monitoring Committee which is charged with the responsibility for ensuring the integrity of the trial. They have and will continue to review all serious adverse events (SAE) and will have the right to trigger an ad hoc safety review if 2 or more similar SAEs are observed that cause concern. In addition, by group (but still blinded) they have and will continue to review events of interest, rates of kidney injury (KDIGO classification of acute kidney injury) and use of renal replacement therapy on an annual basis. In addition, they will review the results of planned interim analyses and provide recommendations regarding the ongoing safety of the VICToRY trial. Two formal interim analysis will be performed to assess increased POD+death in the vitamin C arm after one-third and two-thirds of the patients are enrolled (see section 2.16).

In summary, recent studies provide us with a strong signal that high-dose intravenous vitamin C may be beneficial in septic patients. While the pre-clinical data related to burns are compelling, the clinical data in burn patients are too sparse to convince clinicians of the therapeutic benefits. We aim to conduct a large scale, multi-center trial of intravenous vitamin C in burns to establish the efficacy of our proposed intervention.

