Once consent is obtained, and necessary baseline data collected for qualifying patients, the study co-ordinator will log on to the web-based randomization system at the Clinical Evaluation Research Unit at Queen's University. The system will confirm eligibility prior to allowing randomization. The system will then provide the study co-ordinator with a patient study number and who will then contact the local pharmacist or delegate with notification of randomization. The unblinded pharmacist or delegate will then access the system to determine the treatment assignment. Allocation will be random and concealed and will be blinded to everyone except the pharmacist at each site who will be responsible for preparing study samples and delivering them to the ICU in a blinded fashion in accordance with the documented study operating procedures. The randomization system, which has proven reliable in several prior RCTs, has a robust audit trail, and will maintain concealment and blinding.

The randomization system will use a computer-generated randomization schedule allocating patients 1:1 to either vitamin C or matching placebo by the method of permuted blocks of random undisclosed size stratified by centre. The study statistician will be responsible for generating the randomization codes and will keep these codes in a password protected file on a private drive on the servers at Kingston Health Science Center. Given the large pragmatic nature of the definitive trial, we will not stratify by additional factors such as burn severity. Since there are no antidotes to Vitamin C, there are no unblinding procedures. Study IP stopping rules are articulated in section 1.5.

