Packed RBCs (volume)												
Plasma (volume)												
Albumin, 5%, 20%, 25%, other (volume)												
Urine output (mL)												
Total fluid volume IN (mL)												
Total fluid volume OUT (mL)												
BURN RELATED PROCEDURES (record from hospital admission to hospital discharge for a maximum of 3 months)												
Date, planned or unplanned, location of procedure, and type of procedure												
PROTOCOL VIOLATIONS (record from randomization to 3 days after last dose of IP)												
Type of violation, SI awareness, action taken												
EVENTS OF INTEREST (record related events that result in stopping IP early, from start of IP to stop of IP)												
New diagnosis of oxalate kidney stone												
Severe hemolysis												

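### Section 1.5 gives two different stopping rules for hemolysis, the Appendix B event row follows the narrower one, and haptoglobin is recorded at its uninformative extreme

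*Combined protocol and SAP*

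**What the plan says.** Section 2.3 names one home for the rules: "Study IP stopping rules are articulated in section 1.5". Section 2.6 also points there for the safety criteria.

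Within section 1.5, hemolysis is treated twice:

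- **Narrative on G6PD deficiency.** Known deficiency is excluded, but "we will not screen eligible patients for G6PD deficiency". Hemolysis is to be monitored and recorded, and "If hemolysis happens during the intervention period, we will stop the study drug and provide standard supportive care". The text then notes that drug-induced hemolysis resolves once the drug responsible is withdrawn.
- **Item 2 of the list on handling safety concerns.** Here "the treating physician will have the right to discontinue study product if the enrolled patient develops a new diagnosis of oxalate kidney stones, severe hemolysis", and the list goes on to other named events. It ends with a catch-all: "any other medical complication such as an SAE that, in the opinion of the treating physician, ongoing use of study product would compromise patient safety".

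Item 3 of that list has the data monitoring committee (DMC) review events of interest by blinded group.

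The Appendix B block for these events is headed "EVENTS OF INTEREST (record related events that result in stopping IP early, from start of IP to stop of IP". Its hemolysis row reads "Severe hemolysis". The daily laboratory block of the same appendix has a yes/no row for clinical suspicion of hemolysis. It records LDH and reticulocytes at their highest, hemoglobin at its lowest and haptoglobin at its highest. Laboratory values are recorded only when ordered as standard of care.

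**The concern.** A stopping rule should have one force and one threshold. Section 1.5 gives two of each. A site that works from item 2, which is the operational list, could go on dosing a patient whose treatment the narrative says will stop.

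This is the stated safeguard for a patient whose G6PD deficiency was never diagnosed. The trial chose not to screen so that treatment could start early, and it relies on stopping the drug if hemolysis appears. Section 2.3 provides no unblinding procedure, so the bedside team must act without knowing the allocation. Section 2.15 plans for more than 40 sites in many countries, and they should all read the same instruction.

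The event form carries the narrower wording forward. If a site follows the narrative and stops for a milder hemolysis, the block meant for related events that end dosing has no row for it. That block is what section 1.5 says the DMC reviews.

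The haptoglobin label is a separate slip in the same monitoring. Of two results on one day, the form keeps the one less likely to show hemolysis.

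**Working it through.** The plan gives no figure on this point, so the check is a comparison of texts.

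**1. The two rules compared (section 1.5).**

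| | Narrative | Item 2 |
|---|---|---|
| Force | Drug will be stopped | Physician has a right to stop |
| Threshold | Hemolysis, no grade given | Severe hemolysis |
| Milder cases | Included | Only through the catch-all, by judgment |

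They differ on 2 points, force and threshold. Neither hemolysis nor severe hemolysis is defined.

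**2. What each rule requires for suspected drug-related hemolysis.**

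- Severe case: the narrative requires a stop; item 2 permits one.
- Milder case: the narrative requires a stop; item 2 permits one if the physician judges that continuing would compromise safety.

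Stopping satisfies both rules in both cases. Continuing is compatible only with item 2. The catch-all widens what is permitted but does not make it an obligation, so it does not reconcile the two.

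**3. Event-of-interest rows in Appendix B against item 2.** The rows are oxalate kidney stone, severe hemolysis, severe acid-base imbalance, severe electrolyte imbalance and refractory hypoglycemia. All 5 correspond to events named in item 2, which joins the acid-base and electrolyte items in one phrase. The number of rows for hemolysis below severe is 0.

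**4. Where a milder hemolysis is still recorded.**

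- The daily suspicion row, Days 1 to 8, covers any grade but records neither severity nor a link to stopping.
- The dosing record includes interruptions.
- Section 2.6 requires the timing and reason for withdrawal from study product to be noted.

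The event is therefore not lost. What is missing is its grade and its place on the list that the DMC is said to review.

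**5. Direction of the laboratory extremes.** In hemolysis LDH and reticulocytes rise, while hemoglobin and haptoglobin fall. This is general physiology; the documents do not state it. Appendix B keeps LDH highest, reticulocytes highest and hemoglobin lowest, so 3 of these 4 markers are taken in the direction of hemolysis. Haptoglobin, kept at its highest, is the 1 that is not. With one result in a day the highest equals the lowest, and with none nothing is recorded. The label therefore changes the data only on days with two or more haptoglobin results.

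**6. Reach into the analyses.** Dosing every 6 hours for 96 hours gives 96 / 6 = 16 doses. The per-protocol analysis in section 2.16 needs all 16, so a patient stopped early leaves it. The primary (modified intention-to-treat) analysis keeps anyone who received some study product, and section 2.6 continues outcome collection after early stopping.

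**The case against.** The strongest reply is that the two texts can be read together. The narrative says what the trial will do. Item 2 protects the physician's authority and forbids no stop. A site would have to overlook an explicit sentence shortly before item 2 in order to continue dosing, and no divergent practice is documented. Leaving severity to clinical judgment also matches the other events in item 2, and restricting events of interest to severe hemolysis is a legitimate choice.

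Part of this stands. Always stopping does comply with both texts, and the lack of a definition is not the main problem. But a site should not have to infer which of two statements binds it. A restriction to severe events also does not fit a block that exists to record related events that ended dosing, when the narrative ends dosing without a grade.

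Three stronger readings are tempting, and the documents do not support them:

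- **That milder hemolysis goes unrecorded.** Step 4 of the working shows otherwise. Nor can this be argued from its absence from the outcome list in sections 2.8 and 2.9. Section 1.5 says that complications "there are several complications that may develop which will be closely monitored as" events of interest or outcomes, and calls acute kidney injury an outcome, yet that list does not name kidney injury either.
- **That the narrative requires a stop for hemolysis of any cause, in conflict with the relatedness condition in Appendix B.** The sentence sits in the G6PD text and is followed by a remark on drug-induced hemolysis. In context it concerns hemolysis attributed to the drug.
- **That a count of undiagnosed G6PD-deficient patients measures the impact.** The documents call the prevalence low and give neither a rate nor a hemolysis frequency. Such a count would also not be the number with milder hemolysis who fall between the two rules.

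On haptoglobin, it is fair to say that no stopping rule or planned analysis uses the value. That limits the consequence but does not make the highest value the right one to keep.

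**Conclusion.** The point holds and is minor. Section 1.5 states two hemolysis rules that differ in force and threshold, and no other section resolves them. The event-of-interest row follows the narrower rule, which leaves a small reporting gap because the same event is recorded elsewhere. Haptoglobin is kept at the wrong extreme, with an effect only on days with two or more standard-of-care results.

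The number of patients affected cannot be calculated from the documents, but it is likely to be small. The earlier sepsis trials that section 1.5 cites mostly did not screen for G6PD deficiency, and it says that no related adverse event has been reported. Nothing shows that sites now act differently, that the DMC is denied the daily data, or that power, type I error or the primary analysis is touched. The conclusion rests on the plain wording of section 1.5 and Appendix B and, for haptoglobin only, on general physiology.

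**What to change.** - **Item 2 of section 1.5.** Carry the narrative's rule into the list, limited to suspected drug-related hemolysis. For example: *Study product will be stopped if hemolysis suspected to be related to study product occurs during the intervention period.* Remove severe hemolysis from the discretionary events. If the safety physicians prefer a severity threshold, define it and use it in both places.
- **Appendix B, events of interest.** Relabel the row *Hemolysis leading to stopping IP (record severity)*.
- **Appendix B, daily laboratory.** Change the haptoglobin entry to *lowest* from now on, without re-extracting past records.

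The cost is protocol and case report form wording and a notice to sites, with no new tests or patients. There are two downsides. A few patients may stop early and leave the per-protocol set. Haptoglobin values before and after the change will follow different rules on days with more than one result, so the date of the change should be kept with the data.

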2. THE PROPOSED TRIAL

2.1 What is the proposed trial design?

We propose a multicenter, double-blind, randomized controlled trial of 666 patients with severe burns randomly allocated to receive 50 mg/kg every 6 hrs for 96 hours of intravenous vitamin C or placebo. As patients recruited into the pilot trial will also be followed up for the phase III endpoints, the patients from the pilot will also contribute to the confirmatory phase III analysis. This approach will use resources in an efficient manner and will allow us to progress swiftly to make the therapy available to patients as early as possible, if it is safe and efficacious. A Schedule of Assessments is included as Appendix B.

2.2 What are the planned trial interventions?

Patients will be allocated to 2 groups: **Vitamin C group:** patients will receive intravenous vitamin C at 50 mg/kg every 6 hrs for 96 hours. **Control group:** patients will receive a similar

amount of placebo (either D5W or saline) delivered in the same manner as the vitamin C. The vitamin C will be sourced locally and prepared in a blinded manner by local research pharmacies. The vitamin C will be diluted in either 0.9% NaCl or D5W to a concentration of ≤ 92 mg/mL. According to stability testing, vitamin C concentration between 36 and 92 mg/mL, diluted in either normal saline or D5W, and stored protected from light at 2-8°C is physically and chemically stable for at least 14 days.⁷⁶ The volume for dilution will be determined based on the patient's pre-burn dry weight to a maximum of 150 kg. Dosing will be calculated based on a weight of 150 kg for patients weighing ≥ 150 kg. The duration of each infusion will be dependent on infusion rate. The infusion rate will not exceed 100 mg/min. Below is a sample table of infusion volumes and durations based on patients with a pre-burn dry weight between 50 and 175 kg, dosed at a maximum of 150 kg:

	Kg	mg	mg	mL	Minutes
Pre-Burn Dry Weight	Dosing Weight	mg/day based on highest dose (200 mg/kg)	mg/dose (q6h)	Volume/dose (max dose of 92mg/mL)	Duration of infusion (max rate of 100mg/min)
50 kg	50	10000	2500	27	25
75 kg	75	15000	3750	41	37.5
100 kg	100	20000	5000	54	50
125 kg	125	25000	6250	68	62.5
150 kg	150	30000	7500	82	75
175 kg	150	30000	7500	82	75

A missed dose administration will be compensated by a make-up dose within 24 hours of the missed dose. Open-label vitamin C to a maximum of 200 mg/day delivered intravenously or 1,500 mg/day enterally will be allowed in study subjects for the purpose of nutrient repletion. There are no excluded medication treatments before or during the trial other than high dose IV vitamin C. There is no 'rescue' medication for study subjects.

We will provide an inventory Drug Accountability Log (DAL) which will be maintained by the unblinded pharmacist at each participating site to document receipt, distribution, and destruction of the locally sourced IV vitamin C. A participant specific DAL will also be provided for each pharmacy team member to record all doses of study product, active or placebo, prepared and administered to each participant.

2.3 What are the proposed arrangements for allocating participants to trial groups?

To influence clinical outcomes and in particular, resuscitation endpoints, high-dose intravenous vitamin C has to be given as early as possible- within hours of admission to the hospital. This will mean the requirement for obtaining fully informed consent prior to initiation of study procedures may be impractical. Many if not all of the patients will be 'incompetent' to provide consent themselves due to their burn or burn-associated illnesses and medications. Most families or legally appointed representatives are not present during those early hours of resuscitation. Accordingly, we will apply for alteration in informed consent in participating sites, outside of the U.S., that allow for alterations, or where applicable, such as in the UK, Germany,

France, and possibly other countries where permitted by national regulations, sites can use a third-party or professional consent process and follow up with next of kin when available. In the U.S., and all other countries where deferred or third-party consent is not allowed, we will obtain consent from the patient or the legally appointed representative or next of kin, when available, and if not available within the first 24 hours after hospital admission, the patient will not be enrolled in the study. We aim to have patients enrolled as soon as possible after admission to hospital (patients will be excluded if present in hospital for more than 24 hours).

Once consent is obtained, and necessary baseline data collected for qualifying patients, the study co-ordinator will log on to the web-based randomization system at the Clinical Evaluation Research Unit at Queen's University. The system will confirm eligibility prior to allowing randomization. The system will then provide the study co-ordinator with a patient study number and who will then contact the local pharmacist or delegate with notification of randomization. The unblinded pharmacist or delegate will then access the system to determine the treatment assignment. Allocation will be random and concealed and will be blinded to everyone except the pharmacist at each site who will be responsible for preparing study samples and delivering them to the ICU in a blinded fashion in accordance with the documented study operating procedures. The randomization system, which has proven reliable in several prior RCTs, has a robust audit trail, and will maintain concealment and blinding.

The randomization system will use a computer-generated randomization schedule allocating patients 1:1 to either vitamin C or matching placebo by the method of permuted blocks of random undisclosed size stratified by centre. The study statistician will be responsible for generating the randomization codes and will keep these codes in a password protected file on a private drive on the servers at Kingston Health Science Center. Given the large pragmatic nature of the definitive trial, we will not stratify by additional factors such as burn severity. Since there are no antidotes to Vitamin C, there are no unblinding procedures. Study IP stopping rules are articulated in section 1.5.

